8.11 Safety Assessments

Safety assessments will be based on changes from baseline of AEs reported by the patients or observed by the Investigator, concomitant medication and blood product use, treatment discontinuation due to AEs, vital signs, ECG, physical examination, laboratory assessments (hematology, blood chemistry), and evaluation of the performance status by the ECOG.

AEs and SAEs will be graded according to the CTCAE, version 5. All AEs (serious and non-serious) occurring between Study Day 1 and 30 days following the last dose of study treatment of each course will be documented in the trial subject's medical records. The following AEs will additionally be documented in the eCRF if:

- Serious (SAE) as defined in 13.2, whether or not related to study drug,
- Related to study drug, regardless of grade and clinical significance,
- Unrelated to study drug but grade ≥ 3 and clinically significant.

AEs and SAEs occurring after 30 days of the last study treatment dose in each course, should only be recorded if considered at least possibly related to study treatment by the local investigator. SAEs and Grade 3 or higher AEs that are ongoing at the end of this period (30 days from last study treatment administration) will be followed until each event is resolved or is assessed as chronic. Serious and nonserious adverse events occurring after the study-specific informed consent is signed but prior to Study Day 1 will be collected only if they are considered by the investigator to be causally related to the study-required procedures.

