9.2 Safety and Tolerability Outcome Measures

Safety outcomes:

1. AEs analyzed by frequency, NCI-CTC grade, and causality
2. Serious Adverse Events (SAEs) and events of special interest (injection site reactions, infections, new malignancy, tumor lysis syndrome)
3. Withdrawal rates, days and reasons for withdrawal
4. Dose modifications and treatment delays
5. Serum chemistry and hematology laboratory values; change from baseline and worst NCI-CTC grade

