AEs will be coded using the Medical Dictionary for Regulatory Activities (MedDRA). Incidence tables will be presented for all AEs by maximum grade graded according to the CTCAE, version 5). AEs, SAEs, deaths on study, AEs assessed as related to study drug and AEs resulting in dose reduction, interruption or discontinuation of study drug will be tabulated. Time-to-onset and duration of selected events will also be tabulated.

Laboratory assessments will be presented in shift tables of baseline grade vs. maximum grade on study, and summarized descriptively.

Study Drug Exposure

The number of days and/or cycles that subjects were exposed to study drug will be summarized.

General statistical considerations

Missing values will not be imputed. Outliers will be identified prior to the analyses of the efficacy endpoints and have to be checked by the study physician. According to the decision of the data management, the statistician and the study physician, outliers will be kept in the database or set to "missing".

Analysis datasets

Full analysis set (FAS)

All efficacy analyses will be conducted with the full analysis set (FAS). The full analysis set consists of all patients who were included in the study.

Per protocol analysis set (PPS)

The secondary dataset for analysis is derived from the per-protocol (PP) population. This dataset includes all trial subjects who were treated without major protocol violations.

Safety analysis set

The safety analysis set comprises all trial subjects who received any IMP or other trial treatment.

Sample size calculation

Based on AZARELA trial results, we assume that approximately 30% of responses due to AZA/DLI effects only might be observed. The objective is to demonstrate a 20% increase in response due to the addition of VENETOCLAX (i.e. from 30% to 50% after 6 cycles of AZA/DLI + VENETOCLAX).

For the phase I, a design "3+3" will be used, the number of subjects required for dose escalation will depend upon the occurrence of DLTs as the study progresses. Approximately 9 - 18 subjects may be enrolled to identify the MTD for venetoclax in combination with azacitidine.

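### Section 8.11 filters which adverse events reach the eCRF, while 10.2 promises tables of all AEs and 13.1 reads as if every event is entered; if 8.11 governs, the tables are an attribution-dependent undercount

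*Protocol*

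**What the plan says.** **Tables promised.** In the safety part of section 10.2: "Incidence tables will be presented for all AEs by maximum grade graded according to the CTCAE, version 5". The same paragraph lists SAEs, deaths and drug-related AEs, and adds that "AEs resulting in dose reduction, interruption or discontinuation of study drug will be tabulated". Section 9.2 has "AEs analyzed by frequency, NCI-CTC grade, and causality" as its first safety outcome. Its second covers SAEs and "events of special interest (injection site reactions, infections, new malignancy, tumor lysis syndrome".

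**Data collected.** Section 8.11 first has all AEs in the reporting window written in the medical record. It then restricts the database: "The following AEs will additionally be documented in the eCRF if" they fall in one of three classes:
- SAEs of any cause;
- events that the investigator attributes to the drug, at every grade;
- among the remainder, only those described as "Unrelated to study drug but grade ≥ 3 and clinically significant".

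**A second collection statement.** Section 13.1 is mixed. One paragraph places AEs, attributable or not, in the source documents, which agrees with 8.11. A later paragraph has the nature, dates, grade, relationship and seriousness of each event recorded on the AE eCRF, with no filter mentioned.

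**The concern.** The final-analysis paragraph of 10.2 ties database lock to completion of the case report forms, so the safety tables draw on what the eCRF holds. If the eCRF follows 8.11, a table titled as covering all AEs will omit some of them, and whether a mild event appears will turn on the investigator's causality judgement. The trial is open label and single arm, so no concurrent group shows how much that judgement removes.

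Toxicity is the phase I primary endpoint (section 5.1) and a secondary endpoint (section 5.2). A reader would take the tabulated incidence as all-cause. The special-interest events in 9.2 are exposed to the same filter, although naming them implies an intention to count them completely.

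**Working it through.** The protocol states no figure for AE incidence or attribution, so the main check is textual: cross the entry rule in 8.11 with the tables in 10.2 and 9.2.

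**Step 1. Every type of event against the entry rule.**

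| Type of AE | Belongs in the 10.2 tables of all AEs | Entered in the eCRF under 8.11 |
|---|---|---|
| Serious, any grade, any cause | yes | yes |
| Non-serious, related, any grade | yes | yes |
| Non-serious, unrelated, grade ≥ 3, clinically significant | yes | yes |
| Non-serious, unrelated, grade ≥ 3, not clinically significant | yes | **no** |
| Non-serious, unrelated, grade 1-2 | yes | **no** |

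Two of the five rows cannot be filled. Three consequences follow:
- Among non-serious grade 1-2 events, the table of all AEs and the table of related AEs contain the same events by construction.
- A patient with a related grade 1 event and a non-serious, unrelated grade 2 event of the same type is counted, but at grade 1, so maximum grade can be understated as well.
- An interruption or dose reduction caused by a non-serious, unrelated low-grade event drops out of the table of AEs leading to such changes.

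**Step 2. Special-interest events.** New malignancy and tumor lysis syndrome would mostly enter as serious or as grade ≥ 3. The loss falls mainly on mild, non-serious infections judged unrelated. Injection site reactions depend on what study drug means in 8.11. The synopsis lists only venetoclax under that heading, section 12.2 places azacitidine in a Study Drug column as a non-investigational product, and 8.11 itself uses both study drug and study treatment.

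**Step 3. What is not touched.** The DLT criteria in 6.2 and 13.17 concern events of grade 3 or 4 and above, and exclude those the investigator attributes to another clear cause. The two missing rows therefore have essentially no bearing on a DLT count. Laboratory toxicity is summarized through shift tables of baseline against maximum grade (10.2) and worst grade (9.2, item 5), outside the AE filter.

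**Step 4. Size.** For one event type in N patients:

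reported rate = (patients with the event − patients whose every occurrence lies in a missing row) / N

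The protocol gives neither count. Purely as an illustration, take N = 48 (the stated maximum treated). Assume 24 patients have an infection of any grade, a true rate of 24/48 = 50%. Assume further that 10% to 50% of those 24 have only non-serious, unrelated grade 1-2 infections:
- 10%: 24 × 0.90 = 21.6, about 22 patients; 21.6/48 = 45%.
- 50%: 24 × 0.50 = 12 patients; 12/48 = 25%.

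Both the 24 and the shares are assumptions. The arithmetic shows how the filter acts, not what it will do in this trial.

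**The case against.** The strongest objection is that 13.1 can be read as putting every event on the AE eCRF. If that paragraph governs, nothing is lost. This stands in part: a reader of 8.11 alone might infer a certain loss, and the protocol supports only an unresolved conflict. Section 8.11 is nonetheless the specific entry rule, and another paragraph of 13.1 agrees with it by placing AEs in source documents. While both texts remain, sites may apply different rules.

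A reader might also infer that all low-grade azacitidine injection site reactions are lost, because the synopsis names only venetoclax as study drug. That reading is strained. Section 12.2 uses the Study Drug label for azacitidine too, 13.4 assesses causality against study treatment, and 9.2 lists injection site reactions, which makes sense only if azacitidine effects are in scope. What remains is a term to tidy.

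A third objection is that 13.4 defines a reasonable possibility broadly: it includes connections that cannot be excluded with certainty, although two supporting features are also required. Many mild events would then count as related and be entered. This reduces the undercount but does not remove it.

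Finally, selective AE collection is a legitimate choice, and 10.2 defers structured analyses to a separate SAP. Both points are fair. A SAP can rename a table to match the data, but it cannot recover events that were never entered.

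**Conclusion.** The point holds as an inconsistency with a conditional consequence. If 8.11 governs, the tables of all AEs and the low-grade special-interest rates are undercounts that depend on attribution. If the broader paragraph of 13.1 governs, there is no undercount, but 8.11 is then wrong as written. Either way the text needs reconciling before data entry. The size cannot be derived from the document. The conclusion assumes that the safety tables are built from eCRF data, as the link between database lock and the case report forms indicates.

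Two wider inferences are not supported. Toxicity being the phase I primary endpoint might suggest that dose finding is compromised, but the missing events lie essentially outside the DLT criteria. Nor does the protocol plan any comparison of AE rates with an outside figure, so a biased comparison is not part of this plan.

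**What to change.** 1. Reconcile 8.11 and 13.1 so that a single eCRF entry rule applies.
2. In 8.11, use study treatment (venetoclax, azacitidine, DLI) consistently in place of study drug.
3. In 8.11, enter the special-interest events listed in 9.2 regardless of grade and relatedness.
4. If the filter stays, replace the reference to all AEs in 10.2 with the set actually collected: serious, related of any grade, or grade ≥ 3 and clinically significant. Report the special-interest events separately as all-cause.

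Items 1, 2 and 4 are wording. Item 3 adds a small amount of eCRF entry for events already documented at site. Entering every Cycle 1 AE would go further, but that is a trade-off in data collection for the sponsor and is not needed to correct the inconsistency. None of these changes affects dosing or patient management.

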3 HYPOTHESIS

Based on AZARELA trial results, we assume that approximately 30% of responses due to AZA/DLI effects only might be observed. The objective is to demonstrate a 20% increase in response due to the addition of VENETOCLAX (i.e. from 30% to 50% after 6 cycles of AZA/DLI + VENETOCLAX). For the phase I, a design "3+3" will be used including between 9 to 18 patients. For the phase II, a two-stage design will be used. Under $H_0=30\%$ and $p_1=50\%$, the study with $\alpha=0.05$ and $\beta=0.2$, if 3 responses or less are observed in the first 14 evaluable patients, there will be no further inclusions (the inclusions would be terminated early), but all patients on treatment and that continue to derive clinical benefit according to the opinion of the investigator while tolerating study-treatment may continue to receive treatment according to the protocol.

If 4 or more responses are observed, 16 additional patients will be included in the study. If 13 responses or more are observed in evaluable patients, further investigation is warranted to compare AZA/DLI and combination of AZA/DLI and VENETOCLAX. We consider that a maximum of 10% of the population may not be evaluable for response and that a total of 48 patients will be needed to address the question.

All patients on treatment and that continue to derive clinical benefit according to the opinion of the investigator while tolerating study-treatment may continue to receive treatment at the cohort-assigned dose level.

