For the phase II, a two-stage design will be used. With the assumption that the AZA/DLI gives 30 % of ORR, with the assumption that AZA/DLI + VENETOCLAX gives 50 % of ORR, and with an alpha risk of 0.05 and a beta risk of 80% with a drop-out of 10%, to confirm the safety and evaluate efficacy, for the phase II, 30 patients should be treated at the optimal dose (27 patients + drop-out of 10%).

Overall, a maximum of 48 patients will be treated: 9 - 18 in phase I and 30 in phase II.

Statistical analysis plan

Analysis will be based on an intent-to-treat basis, whether or not the patient receives the protocol treatment.

It will be performed once the sample size has been reached in each group, separately.

It will be based on the computation of response rate, with 95% confidence interval.

Randomization / Stratification

Not applicable for this trial.

Methods of Statistical analysis

A summary of the planned statistical analyses are described. Structured analyses will be specified in a separate statistical analysis plan (SAP) prior to the end of the data management process and before receiving final study data. If analyses should be conducted deviating from the following descriptions, these deviations also will be specified in the SAP prior to receiving final study data.

Descriptive Statistics

For continuous variables mean, standard deviation (SD), median, interquartile range, minimum and maximum will be presented.

For categorical variables absolute and relative frequencies will be presented.

Interim analysis

An interim analysis is planned during the phase II to evaluate the effectiveness of treatment.

If 3 responses or less are observed in the first 14 evaluable patients, there will be no further inclusions (the inclusions would be terminated early), but all patients on treatment and that continue to derive clinical benefit according to the opinion of the investigator while tolerating study-treatment may continue to receive treatment according to the protocol.

If 4 or more responses are observed, 16 additional patients will be included in the study.

Final analysis

The final report of the study and the compilation of the statistical report will be performed within 12 months after completion and correction of all case report forms (database lock).

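### Section 10.2 labels the 80% power as a beta risk, contradicting section 3; correcting the label alone still leaves an alpha and power pair that the written rule does not have

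*Protocol*

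**What the plan says.** Protocol section 10.2, under the sample size calculation, sets out the phase II comparison: "With the assumption that the AZA/DLI gives 30 % of ORR", and "with the assumption that AZA/DLI + VENETOCLAX gives 50 % of ORR". It then gives the error rates: "with an alpha risk of 0.05 and a beta risk of 80% with a drop-out of 10" percent. From these it arrives at 27 patients plus a 10% allowance, which makes 30.

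Protocol section 3 describes the same hypothesis and the same two stages with "the study with $\alpha=0.05$ and $\beta=0.2".

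The decision rule is spread over both sections. Both give the first stage: "If 3 responses or less are observed in the first 14 evaluable patients, there will be no further inclusions". Both give the second: "If 4 or more responses are observed, 16 additional patients will be included in the study". Only section 3 gives the final criterion: "If 13 responses or more are observed in evaluable patients, further investigation is warranted".

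Neither section says whether alpha is one-sided or two-sided. Section 10.2 takes the 10% loss out of the 30. Section 3 also allows for up to 10% not evaluable, but does not say how many evaluable patients the criterion of 13 responses refers to.

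**The concern.** Beta is the probability of missing a combination that truly has the target response rate, so a beta risk of 80% and a beta of 0.2 cannot both describe one design. Section 10.2 is where an ethics committee, or whoever writes the SAP, would look for the power of phase II, and the figure printed there is wrong.

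The obvious repair is to turn 80% into 20%. The sentence would then claim alpha 0.05 and power 80% from 27 evaluable patients out of 30. Whether the written rule supports that claim has to be checked as well. Otherwise the correction replaces a visible slip with a statement that looks sound and is not.

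**Working it through.** **Inputs.** Null rate 30%, target rate 50%, alpha 0.05 and beta 80% (section 10.2); beta 0.2 (section 3); first stage 14 patients, continue with 4 or more responses; second stage 16 patients (both sections); success with 13 or more responses (section 3); 27 patients plus 10% (section 10.2). Alpha is taken as one-sided, the usual reading of a single-arm rule of this form.

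**The plan's own figure.** The allowance for loss reproduces: 27 / (1 − 0.10) = 30.

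**Does beta 80% fit the planned size?** The one-sample normal approximation is

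n = [(z(1−alpha) × √(p0(1−p0)) + z(power) × √(p1(1−p1))) / (p1 − p0)]².

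With one-sided alpha 0.05 and power 20%, n = [(1.645 × 0.458 − 0.842 × 0.5) / 0.2]² ≈ 2.8. Two-sided alpha and other variance choices give at most 7.8. An exact search over two-stage designs needs 6 or 7 patients. A design with 20% power would therefore need fewer than 10 patients, not 27 to 30.

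**Does beta 0.2 fit the written rule?** With X1 responses among the first 14 and X2 among the remaining n2,

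P(success) = Σ over x = 4 to 14 of P(X1 = x) × P(X2 ≥ 13 − x).

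Take n2 = 16 and a true rate of 50%. The largest terms are x = 7 (0.2095 × 0.8949 = 0.187), x = 8 (0.1833 × 0.9616 = 0.176) and x = 6 (0.1833 × 0.7728 = 0.142). All terms sum to 0.8135, so beta = 1 − 0.8135 = 0.1865. This agrees with section 3 and not with section 10.2.

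**What alpha comes with that power?** The same sum at a true rate of 30% is 0.0829.

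**Other readings of the final analysis.** The first stage is kept at 14; for 27 evaluable patients the second stage has 13.

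| Evaluable | Success at | Type I error at 30% | Power at 50% |
|---|---|---|---|
| 30 | ≥ 13 | 8.3% | 81.4% |
| 30 | ≥ 14 | 4.0% | 70.5% |
| 27 | ≥ 13 | 3.6% | 64.8% |
| 27 | ≥ 12 | 7.9% | 77.6% |

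No row comes near 20% power, and no row has both a type I error of at most 5% and power of at least 80%. An exhaustive search found no two-stage design with 30 or fewer patients that meets both for 30% against 50%. The smallest maximum size is 39 (minimax design); the design with the smallest expected size under the null needs up to 46.

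**The case against.** The best defence is that this is a slip in one word. The value 80% is the customary power, section 3 prints the right beta, and the planned size makes sense only for high power. The 30 patients, the two stages, the stopping limit and the threshold of 13 all stay the same when the word is corrected. Section 3 also carries the complete rule, including the final threshold that section 10.2 omits, so a careful reader is unlikely to be misled. All of this stands and keeps the point minor.

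A reader might infer from section 10.2 that the trial is powered at only 20%, or that the sample size was derived from that figure. The documents do not support either reading: the written rule has 81.4% power with 30 evaluable patients, and 20% power would need fewer than 10 patients. The gap between 80% and 18.6% measures a mislabelled number, not a loss of power.

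The opposite inference is also tempting: that once the label is corrected, the calculation is confirmed. That does not hold either. The 81.4% that supports section 3's beta comes with a type I error of 8.3%, and it requires all 30 patients to be evaluable, whereas section 10.2 counts on 27.

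**Conclusion.** The point holds as a minor correction. The beta risk of 80% in section 10.2 is wrong: it contradicts section 3 and the written rule, whose beta is 18.6% with 30 evaluable patients. It is evidently the power mislabelled, and it affects neither the sample size nor the decision rule.

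Correcting the label does not validate the alpha 0.05 and 27-to-30-patient calculation around it. The rule gives either adequate power with too large a type I error (81.4% and 8.3% at 30 evaluable) or an acceptable type I error with too little power (3.6% and 64.8% at 27 evaluable).

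These figures assume a one-sided test, exact binomial probabilities, a full first stage of 14 evaluable patients, and the threshold of 13 kept whatever the final number evaluable. The documents state neither the sidedness nor what happens to the threshold when patients are not evaluable.

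**What to change.** In section 10.2, replace the beta figure by *a beta risk of 20% (power 80%)*. In the same sentence, repeat the final threshold and state what the rule delivers and on how many evaluable patients. For example: *with 14 + 16 evaluable patients, stopping at 3 or fewer responses in 14 and declaring success at 13 or more in 30, the exact power is 81.4% at 50% and the exact one-sided type I error is 8.3% at 30%; if only 27 are evaluable and the threshold of 13 is kept, these are 64.8% and 3.6%*. Give 0.05 and 80% as nominal targets only, and align the alpha in section 3 with this text.

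This is a text change at the next amendment, with no effect on enrolment, the stopping limit or the threshold. If the sponsor wants the rule actually to meet 5% and 80%, that is a separate design decision with a real cost: 39 or 46 patients in phase II in place of 30.

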10.2 Efficacy Endpoints

Efficacy will be evaluated by the investigator according to the 2006 IWG response criteria in MDS and for AML according to AML in Adults: 2017 ELN Recommendations from an International Expert Panel Revised (Döhner et al., 2017).

The analyses for efficacy will be performed for the following endpoints.

Overall Response Rate

The proportion of subjects with overall response ($OR = CR + mCR + PR + HI$) will be calculated. The 95% confidence interval for OR rate based on binomial distribution will be constructed.

Complete Remission Rate

The proportion of subjects with complete remission (CR) will be calculated. The 95% confidence interval for CR rate based on binomial distribution will be constructed.

Marrow Complete Remission Rate

The proportion of subjects with mCR with or without hematological improvement will be calculated. The 95% confidence interval for mCR rate based on binomial distribution will be constructed.

Partial remission (PR)

The proportion of subjects with PR with or without hematological improvement will be calculated. The 95% confidence interval for PR rate based on binomial distribution will be constructed.

Hematologic Improvement

The proportion of subjects with HI (erythroid/platelet/neutrophil responses) will be calculated. The 95% confidence interval for the rate of HI based on binomial distribution will be constructed.

Time to AML Transformation

Time to AML transformation will be defined as the number of days from the date of the first dose of study drug to the date of documented AML transformation. AML transformation will be defined as the presence of blast count $\geq 20\%$ in either the peripheral blood or bone marrow. Time to AML transformation will be summarized as median (range). Subjects who do not show transformation to AML will not be included in the analysis.

Duration of Response

Duration of response (DOR) will be defined as the number of days from the date of first response (CR, mCR, PR or HI) to the earliest documentation of progressive disease (PD). Duration of response will be analyzed by Kaplan-Meier methodology. Median DOR will be calculated and 95% confidence interval for median DOR will be presented.

If the response is still ongoing at the time of analysis, the subject's data will be censored at the date of the subject's last available disease assessment. For subjects who never experience a response, the subject's data will not be included in the analysis.

Overall Survival

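### Phase II is decided by a count in section 3 but analysed by a 95% confidence interval in section 10.2; the two disagree at 13 and 14 of 30, and neither delivers alpha 0.05 with 80% power

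*Protocol*

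**What the plan says.** Section 3 (Hypothesis) tests 30% against 50% with alpha 0.05 and beta 0.2. Inclusion stops if 3 or fewer of the first 14 evaluable patients respond; otherwise 16 more are added. The final reading is a count: "If 13 responses or more are observed in evaluable patients, further investigation is warranted", the next step being a comparison of AZA/DLI with and without venetoclax.

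Section 10.2 uses the same rates ("With the assumption that the AZA/DLI gives 30 % of ORR"; "with the assumption that AZA/DLI + VENETOCLAX gives 50 % of ORR") and gives the error rates as "with an alpha risk of 0.05 and a beta risk of 80% with a drop-out of 10" per cent. The beta of 80% is evidently a slip for 80% power, since section 3 has beta 0.2. The section repeats the 14-patient rule and the 16 additional patients, but not the threshold of 13. Under its paragraph on the statistical analysis plan it says: "It will be based on the computation of response rate, with 95% confidence interval". For the overall response rate it says: "The 95% confidence interval for OR rate based on binomial distribution will be constructed". It specifies neither the type of binomial interval nor any allowance for the interim stop. Both sections state the aim in the same terms: "The objective is to demonstrate a 20% increase in response due to the addition of VENETOCLAX".

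**The concern.** A sample size is tied to the rule that will be applied to the data. Here the size belongs to a one-sided count rule with an interim stop, while the section that prescribes the analysis rests on an ordinary 95% interval. A two-sided 95% interval judges 30% at 2.5% one-sided, so it is stricter than the count. If 13 or 14 patients respond, one reader can call the trial positive under section 3, and another can note that the reported interval does not exclude the AZA/DLI rate that the trial set out to exceed. The protocol gives no way to settle this in advance. The stated alpha and power also need to belong to some rule that the trial will actually use, and it should be checked whether they do.

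**Working it through.** **Inputs.** p0 = 0.30, p1 = 0.50, alpha 0.05, power 80% (sections 3 and 10.2). Stage 1: n1 = 14, continue at 4 or more. Stage 2: n2 = 16, total 30 (both sections). Final threshold r = 13 (section 3 only). Assumption: all 30 patients enter the final count.

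**Formula.** The probability of a positive result at true rate p is the sum over x = 4 to 14 of P(X1 = x) × P(X2 ≥ r − x), where X1 is binomial(14, p) and X2 is binomial(16, p). At p = 0.30 this is the one-sided type I error; at p = 0.50 it is the power.

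**The plan's own rule first, then the alternatives.**

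| Final threshold | Type I error (p = 0.30) | Power (p = 0.50) |
|---|---|---|
| 13 or more (section 3) | 8.3% | 81.4% |
| 14 or more | 4.0% | 70.5% |
| 15 or more | 1.7% | 57.1% |

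The stated power is reproduced at 13; the stated alpha is not. At 14 the alpha is met and the power is not. Searching all two-stage designs for one-sided alpha 0.05 and 80% power, the smallest total is 39, so 30 patients cannot meet both.

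**What the 95% interval says at the same counts.** The exact (Clopper-Pearson) lower limit is the 2.5% quantile of Beta(x, 31 − x). The Wilson lower limit is shown for comparison.

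| Responses | Exact 95% CI | Wilson 95% lower limit |
|---|---|---|
| 13/30 | 25.5% to 62.6% | 27.4% |
| 14/30 | 28.3% to 65.7% | 30.2% |
| 15/30 | 31.3% to 68.7% | 33.2% |

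The exact interval first excludes 30% at 15 responses, and the Wilson interval at 14. Used as the decision, they would have the power in the first table: 57% and 70.5%.

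**How often count rule and exact interval disagree.** This is the chance of 13 or 14 responses after passing stage 1, the difference between the rows for 13 and 15:
- true 50%: 81.4% − 57.1% ≈ 24%
- true 30%: 8.3% − 1.7% ≈ 7%

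**Does the interim stop matter for the interval?** Very little. One-sided 5% lower limits, ordinary exact against two-stage ordering: 27.87% and 27.94% at 13/30; 30.85% and 30.88% at 14/30. For the 95% interval at 14/30: 28.34% and 28.37%. All shifts are below 0.1 point.

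**Range for the number analysed.** Section 10.2 also describes the 30 as 27 plus 10% drop-out. With 27 in the final count (same stage 1), 13 or more gives 3.6% and 64.8%, and 12 or more gives 7.9% and 77.6%. The exact 95% interval first excludes 30% at 14/27, with power 50.0%. Alpha and power are again not met together.

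**The case against.** The strongest reply is that no conflict exists. The protocol has one decision rule, the count in section 3, and section 10.2 only describes estimation. A count rule for going forward, reported beside a descriptive 95% interval, is usual in single-arm phase II trials. An interval that contains the null rate at the lowest passing count follows from pairing a one-sided rule with a two-sided interval. A positive result here leads only to a further comparison, and interval details normally belong in the separate SAP.

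Much of this stands. A reader might infer that the trial's real power is 57%. The documents do not support that: nowhere do they require the interval to exclude 30%. The figure needs that added criterion and also an exact interval, whereas section 10.2 says only that the interval is binomial. A reader might also infer that ignoring the interim stop invalidates the interval; the shift of less than 0.1 point shows that it does not.

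Two things remain. Section 10.2 goes further than reporting an interval: it makes the interval the basis of the analysis, drops the threshold and states an aim of demonstrating an increase. An SAP would inherit that ambiguity. And even if the count alone governs, its type I error is 8.3%, not 0.05.

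One caveat: the overall response in section 10.2 also counts marrow CR and hematologic improvement, whereas the primary endpoint in section 9.1 is CR or PR for MDS and CR for AML. The interval quoted for overall response is therefore not strictly the interval for that primary endpoint. The general sentence on the analysis does not depend on this.

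**Conclusion.** The concern holds as an unresolved choice between two readings, together with operating characteristics that fit neither. The count and the exact 95% interval disagree at 13 and 14 of 30, which has a 24% chance if the true rate is 50% and 7% if it is 30%. With 30 patients, every candidate threshold misses either the stated alpha or the stated power. Only the threshold of 13 is actually written in the protocol, and its figures are 8.3% and 81%. The 57% is what would follow if the sponsor let an exact two-sided 95% interval decide; it is not the power of the trial as written.

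These results assume 30 patients in the final count, the 3-of-14 stop applied as stated, and alpha read as one-sided. The protocol does not state the sidedness; a two-sided reading would make 8.3% compare less favourably still.

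**What to change.** In section 10.2, state that the two-stage count rule is the phase II primary decision, name its final threshold and give the figures that belong to it. Two options need no extra patients:

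- keep 13 of 30, and restate one-sided alpha as about 8% with power 81%; or
- use 14 of 30, and restate alpha as 4.0% with power about 70%.

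Section 3 should carry the same threshold and figures. Label the two-sided 95% interval as descriptive. If 14 is chosen, a two-sided 90% exact interval agrees with the rule (lower limit 30.8% at 14/30, 27.9% at 13/30). It would not agree with a threshold of 13. Two-stage ordering for the interval is optional.

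If the sponsor prefers the two-sided 95% interval to decide, section 10.2 should say so, name the interval method, and restate the power as about 57% (exact) or 71% (Wilson).

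The cost is wording in sections 3 and 10.2 and in the SAP. The downside is that the stated alpha or the stated power becomes less favourable.
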